8.4. Subject Replacement

Subjects who do not complete the study may be replaced, at the sponsor’s discretion to ensure that the study is fully populated, unless a stopping rule precludes replacement. Replacement subjects will receive the same treatment assignment as the subject they are replacing. Each enrolled subject may only participate in this study once. The study is designed to have 12 subjects on active treatment and 6 subjects on placebo to complete the study.

9. STUDY DRUG MATERIALS AND MANAGEMENT

9.1 Investigational Product

The investigational drug product, CRV431, is supplied as 75 mg softgel capsules without marking. The study drug details are presented in [Table 4](#).

Table 4 Investigational Product

	Investigational Product
Product Name:	CRV431 active pharmaceutical ingredient
Dosage Form:	Softgel capsule
Unit Dose	75 mg
Route of Administration	PO
Physical Description	[REDACTED]
[REDACTED]	[REDACTED]
[REDACTED]	[REDACTED]
[REDACTED]	[REDACTED]
[REDACTED]	[REDACTED]

9.2 Placebo

The placebo for this study utilizes the same formulation, white opaque, oblong softgel capsule without marking and without the active ingredient of CRV431 drug substance.

9.3 Study Drug Packaging and Labeling

Study supply will be packaged in blister packs, containing 6 softgel capsules per pack. All study supplies will be labeled as “New Drug – Limited to United States Federal Law to Investigational Use.”

9.4 Study Drug Storage

CRV431 softgel capsules and placebo should be stored between 20°C to 25°C or 68°F to 77°F. Excursions are permitted to 15°C to 30°C or 59°F to 86°F.

9.5 Study Dug Preparation

No preparation will be required for the CRV431 softgel capsules.

9.6 Study Drug Accountability

The Investigator or their designee, must maintain accurate records demonstrating dates and amount of drug received, in what condition the drug was received, to whom it was dispensed (subject-by-subject accounting) and must account of any drug accidentally or deliberately destroyed.

Drug accountability should be completed for CRV431 and placebo during this study.

9.7 Study Drug Handling and Disposal

During the treatment period of the study, CRV431 or placebo will be supplied by a pharmacist or investigator designee responsible for study drug administration and accountability. On study visit days, treatment may only be administered under the supervision of the investigator or site designee(s).

Any used, expired, or non-usable study drug can be destroyed on-site as per the sites standard operating procedures with approval of the sponsor. If study drug cannot be destroyed on-site, it must be returned to the sponsor or designee.

10. PHARMACOKINETIC ASSESSMENTS

10.1. Blood Sample Collection

Whole blood collection procedures are outlined in the Laboratory Procedures Manual. Collection times for PK sampling periods are outlined in Table 6.

10.2. Sample Handling and Shipment

Instructions for specimen sampling, handling, and shipment are provided in the Laboratory Procedures Manual. Samples may be stored for up to 20 years.

10.3. Sample Analysis

Whole blood PK samples will be analyzed for the quantitative concentrations of CRV431 using a validated liquid chromatography/tandem mass spectroscopy (LC-MS/MS) assay. Qualitative analysis will also be performed on the whole blood PK samples of CRV431 for its major metabolites.

10.4. Whole Blood Pharmacokinetic Parameters

Pharmacokinetic parameters for the measurement of CRV431 and its metabolites will be performed from whole blood and are shown in Table 5.

Table 5: Pharmacokinetic Parameters

Parameter	Definition
[REDACTED]	[REDACTED]
[REDACTED]	[REDACTED]
[REDACTED]	[REDACTED]
[REDACTED]	[REDACTED]
[REDACTED]	[REDACTED]
[REDACTED]	[REDACTED]
[REDACTED]	[REDACTED]
[REDACTED]	[REDACTED]
[REDACTED]	[REDACTED]
[REDACTED]	[REDACTED]
[REDACTED]	[REDACTED]
[REDACTED]	[REDACTED]
[REDACTED]	[REDACTED]
[REDACTED]	[REDACTED]
[REDACTED]	[REDACTED]
[REDACTED]	[REDACTED]
[REDACTED]	[REDACTED]
[REDACTED]	[REDACTED]

[REDACTED] No PK parameters will be calculated for subjects with 2 or fewer consecutive time points with detectable concentrations. Individual and mean whole blood concentration time curves (both linear and log-linear) will be

[REDACTED]

Table 6: Pharmacokinetic Sampling Schedule

Day	Day 1				Day 14	Day 28			
Time (h)	Pre-dose	2.0	4.0	8.0	312 (Pre-dose)	Pre-dose	2.0	4.0	8.0
Whole blood (PK)	X	X	X	X	X	X	X	X	X
Plasma (f_u)	X	X				X	X		

Abbreviations: f_u , fraction unbound; h, hour; PK, pharmacokinetic(s).

11. ASSESSMENT OF SAFETY

11.1. Safety Parameters

11.1.1. Demographic

Demographic details will be collected at Screening only.

11.1.2. Vital Signs

Vital sign assessments will comprise of blood pressure, heart rate, temperature, and respiratory rate measurements. Blood pressure will be measured with a standard mercury sphygmomanometer or an automated oscillometric blood pressure monitor, after the subject has been resting in a supine position for at least 5 minutes. Heart rate will be measured by an automated vital signs machine. Respiratory rate will be measured only if medically indicated. Vital signs will be performed for all subjects at the time points indicated in [Table 3](#), or as applicable.

11.1.3. Weight and Height

Weight and height will be assessed at the Screening visit only.

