5.4. Risks and/or Benefits to Subjects

This is the first study of CRV431 in subjects with presumed NASH F2/F3 fibrosis. As this is a Phase 2a trial designed to evaluate safety, PK and biomarkers of fibrosis, subjects who participate in this study are not expected to derive any clinical benefit over the course of the 28-day study. Subsequently, liver biopsies for entry are not required.

Currently, there is no standard of care for NASH patients although life-style intervention including weight loss and alterations in diet are routinely recommended with bariatric surgery for overweight patients (see American Association for the Study of Disease Guidelines for NAFLD). Nonclinical studies conducted by the sponsor to support the Investigational New Drug (IND)

[REDACTED]

[REDACTED]

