6.4. Study Endpoints

6.4.1. Safety Endpoints

Safety and tolerability parameters, including AEs, SAEs, AEs of special interest, physical examinations including weight and height, concomitant medications, laboratory assessments including blood chemistry, hematology and coagulation, urinalysis, pregnancy screening, ECG, and vital sign assessments, will be determined.

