7.1.3. Follow Up Period

After completion of the treatment period, the subjects will be monitored for additional 14 days. A visit window of ± 2 days will be allowed for the Day42/EOS visit.

Subjects who do not complete the study may be replaced within a dosing cohort, unless a stopping rule precludes replacement. Safety criteria for dose adjustments or stopping rules are provided in [Section 7.5](#).

The overall study design of all scheduled procedures is shown in [Table 3](#).

Table 3: Schedule of Events

Procedure	Screening (Day -30 to -2)	Day -1	Day 1	Day 2	Day 7 (±1)	Day 14 (±1)	Day 28 (+2)	EOS/ Day 42 (±2)	ET ^a
Informed Consent ^b	X								
Demographics	X								
Weight and height	X								
HIV, HBV, HCV tests	X								
Physical exam	X								
Medical history	X								
Inclusion/exclusion	X	X							
Randomization		X							
Pregnancy test ^c	X	X						X	X
FSH	X								
Drugs of abuse and alcohol screen	X	X							X
Vital signs ^d	X	X	X	X	X	X	X	X	X
ECG ^e	X	X	X	X	X	X	X	X	X
Blood chemistry ^f	X	X	X	X	X	X	X	X	X
Hematology and Coagulation	X	X	X	X	X	X	X	X	X
Urinalysis	X	X	X	X	X	X	X	X	X
PK ^g			X			X	X		X ^h
Fraction Unbound ^g			X				X		
ELF Score	X						X		

^k On Day 1 and Day 28, subjects will fast overnight for at least 8 hours, will take CRV431 or matching placebo and will fast for an additional 2 hours following receipt of study drug. On subsequent days subject will fast overnight for at least 8 hours, will take CRV431 or matching placebo and will fast for an additional 30 minutes following receipt of study drug.

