11.1.4. Physical Examination and Medical History

Physical examinations will be performed at Screening. Additional examinations may be performed throughout the study, if considered medically necessary. The examinations will include the following body systems: general appearance; eyes, ears, nose, and throat; head and neck; chest and lungs; cardiovascular; abdomen; musculoskeletal; lymphatic; dermatologic; neurologic; psychiatric; and extremities.

A detailed medical history will be collected at the Screening visit only.

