2.2 Endpoints

2.2.1 Study Endpoints

2.2.1.1 Safety Endpoints

Safety and tolerability parameters, including AEs, SAEs, AEs of special interest, physical examinations including weight and height, concomitant medications, laboratory assessments including blood chemistry, hematology and coagulation, urinalysis, pregnancy screening, ECG, and vital sign assessments, will be determined.

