7.6 Physical Examination

A listing of physical examination abnormalities will be provided.

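### Weight is listed as a safety parameter but measured only at Screening, and physical examination after Screening is for cause only, so weight change cannot be assessed and examination findings cannot be compared systematically between arms.

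*Combined protocol and SAP*

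**What the plan says.** The safety endpoint list in protocol 6.4.1 includes "physical examinations including weight and height, concomitant medications". The synopsis (Criteria for evaluation, Safety) has the same item, and SAP 2.2.1.1 repeats it: "Safety and tolerability parameters, including AEs, SAEs, AEs of special interest, physical examinations including weight and height". The first primary objective (protocol 6.1, SAP 2.1.1) is safety and tolerability against placebo over 28 days of dosing.

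On timing, protocol 11.1.3 says "Weight and height will be assessed at the Screening visit only". Protocol 11.1.4 says "Physical examinations will be performed at Screening" and permits further examinations during the study when they are medically necessary.

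On analysis, SAP 5.3 summarises screening weight, height and BMI with the demographics. SAP 7.4 plans change from baseline for blood pressure, heart rate, temperature and respiratory rate, but not weight. For the examination, SAP 7.6 offers one output: "A listing of physical examination abnormalities will be provided".

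**The concern.** A parameter listed for evaluating safety against placebo needs at least one value after dosing starts, and weight has none. The examination can produce post-dose data, but only for subjects whom an investigator chooses to examine again. Protocol 7.3.3 leaves the investigator and sponsor unblinded, so that choice may depend on knowing the treatment.

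The gap also affects how the liver data are read. The protocol regards weight as relevant to this disease: section 5.4 notes that "life-style intervention including weight loss and alterations in diet are routinely recommended", and exclusion criterion 20 bars subjects who lost more than 5% in the 3 months before randomization. Fibrosis biomarkers are a secondary objective (6.2), and a fall in ALT or AST is an exploratory one (6.3). If either moves, the trial will hold no data to show whether weight moved with it.

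**Working it through.** The plan states no figure to reproduce. The check compares what is listed with what is scheduled and analysed.

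**Scheduled assessments, from Table 3.** The table has nine columns: Screening, Day -1, Days 1, 2, 7, 14 and 28, EOS/Day 42, and ET. Two precede the first dosing day, which leaves 9 − 2 = 7 where a post-dose value could be taken.

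| Assessment | Columns marked, of 9 | From Day 1 on, of 7 | SAP change from baseline |
|---|---|---|---|
| Weight and height | 1 (Screening) | 0 | None |
| Physical examination | 1 (Screening) | 0, plus for-cause | None; listing only |
| Vital signs | 9 | 7 | Yes (SAP 7.4) |
| ECG | 9 | 7 | Yes (SAP 7.5) |
| Chemistry; hematology and coagulation; urinalysis | 9 each | 7 each | Yes (SAP 7.3) |

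The text I worked from lacks part of Table 3, but the weight and examination rows are present and agree with 11.1.3 and 11.1.4.

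**Count of weights.** Planned subjects: 12 + 6 + 12 + 6 = 36. Planned pre-dose weights: 36 × 1 = 36. Planned post-dose weights: 36 × 0 = 0. Unlike 11.1.4, section 11.1.3 has no clause allowing later measurements.

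**Age of the only weight.** Screening may fall up to 30 days before Day 1, or up to 60 days when a retest is awaited (7.1.1). Randomization is on Day -1, when weight is not repeated. At nominal Day 28, which is 27 days after Day 1, the only weight could be 30 + 27 = 57 days old, or 60 + 27 = 87 days old in the retest case.

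**Whether the SAP closes the gap.** It does not. SAP 4.6 defines baseline as the last non-missing value before first dose, so the screening weight would be the baseline, with no later value to set against it. SAP Appendix B proposes no weight or examination table apart from demographics. SAP 6.2 and 6.3 are redacted, but no analysis there could use a weight that was never scheduled.

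**Physical examination.** Three routes can carry post-dose findings: for-cause examinations (11.1.4), the abnormality listing (SAP 7.6), and adverse events noted by observation (11.4). Information can therefore arise. What is missing is a common set of examined subjects at a common time in each arm, which a comparison with placebo needs.

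**The case against.** The strongest reply is that 6.4.1 lists assessments and does not define change endpoints. Height, concomitant medications and pregnancy screening appear in the same sentence, and none of them is analysed as a change. On this reading protocol and SAP agree: weight is a baseline descriptor (SAP 5.3) and a covariate (protocol 12.3.2), and the only fault is a loose label. This is fair for height, and it shows that no change-in-weight endpoint was explicitly promised. It does not explain why an item measured once before dosing belongs among parameters meant to evaluate safety against placebo.

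The second reply concerns confounding. Subjects are randomized 2:1 to placebo within each dose level, recent weight loss is excluded, the protocol sets no weight intervention, and ALT/AST is only exploratory. Randomization does mean that weight change unrelated to treatment should not differ systematically between active and matching placebo. But groups of 12 and 6 leave ample room for chance imbalance. The planned Cohort A versus Cohort C comparison (synopsis, Statistical methods) has less protection still, because Cohort C starts only after DSMB review of Cohort A and B data (12.3.1). The documents give no figure for expected weight change over 28 days, so the point is that it cannot be checked, not that it is likely to be large.

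A reader might also infer that no on-treatment change in physical examination can be assessed at all. The documents do not support that, because for-cause examinations are allowed, their abnormalities are listed, and observed findings are recorded as adverse events.

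**Conclusion.** The point holds in full for weight and in part for physical examination. On-treatment weight change cannot be assessed in any arm: none of the 36 planned subjects has a scheduled weight after Screening. For physical examination, post-dose data will exist only for subjects selected by unblinded investigators, so no systematic comparison between arms is possible.

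A reader might go further and conclude that the primary safety objective cannot be met, or express the gap as a share of an endpoint lost. Neither follows. Weight and examination are items in a longer list. The objective rests mainly on adverse events collected from consent to EOS/ET, and on laboratory tests, ECG and vital signs marked in every column of Table 3. The gap is a real but limited weakness that should be repaired because repair is cheap.

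The conclusion assumes that SAP Appendix A, which is not in the text I worked from, repeats the schedule in protocol Table 3, and that sites do not record weights outside the protocol.

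**What to change.** - **Weight.** Add it at Day 28 and Day 42/ET in Table 3 and 11.1.3, and ideally at Day -1, which would become the baseline under SAP 4.6 without further change. Day 28 and Day 42 would give up to 36 × 2 = 72 planned post-dose weights, with ET covering early leavers.
- **SAP.** Summarise weight and its change from baseline by treatment group and visit, for example with vital signs in SAP 7.4, and add the table to Appendix B.
- **Physical examination.** Optionally schedule a brief one at Day 28 or Day 42/ET. Otherwise describe it in the synopsis, 6.4.1 and SAP 2.2.1.1 as a screening and for-cause assessment.
- **Height.** Treat it as a baseline characteristic.

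Deleting weight from the lists would remove the inconsistency but leave weight change unobserved, so it is not a sufficient repair. The cost is a few minutes at visits that already take place, one CRF field and one table. HbA1c is already repeated at Day 28, EOS and ET (11.1.6.2), so no new visit is needed.

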11.1.4. Physical Examination and Medical History

Physical examinations will be performed at Screening. Additional examinations may be performed throughout the study, if considered medically necessary. The examinations will include the following body systems: general appearance; eyes, ears, nose, and throat; head and neck; chest and lungs; cardiovascular; abdomen; musculoskeletal; lymphatic; dermatologic; neurologic; psychiatric; and extremities.

A detailed medical history will be collected at the Screening visit only.

11.1.5. Electrocardiogram

Twelve-lead ECGs will be performed after the subject has been supine for 5 minutes, and 1½ to 3 hours after the morning dose. On Day 1 and Day 28, ECGs will be performed prior to the 2 hr. PK draw. Electrocardiograms performed on non-dosing Days should be completed within the same time window as the ECGs that were done 1½ to 3 hours after the time the morning doses were administered. These ECG schedules will therefore be close to the time of day the previous post-dose ECGs were obtained. The timing of the ECG may be adjusted to C_{max} values as new data becomes available. All ECGs should be interpreted by the investigator or qualified designee within 12 hours of the time the ECGs were performed. Electrocardiograms will be performed for all subjects at the time points indicated in [Table 3](#), or as applicable.

11.1.6. Laboratory Assessments

All samples should be collected and shipped as directed in the Laboratory Procedures Manual.

Routine clinical laboratory testing will be performed for all subjects at the time points indicated in [Table 3](#), or as applicable. Samples may be stored up to 20 years.

If the investigator believes that access to laboratory data is medically indicated and that a delay in access to central laboratory safety results would pose a potential safety risk to the subject, the sample will be split; a portion will be sent to the local laboratory for appropriate laboratory tests, and the other portion will be sent to the central laboratory for routinely scheduled testing.

Samples will be collected and stored for testing for additional safety or PK testing as necessary.

11.1.6.1. Hematology and Coagulation

Samples will be collected before study drug dosing and after at least an 8-hour fast; however, in case of an early termination or recheck, subject fasting is not required prior to sample collection. The following will be performed:

- Total white blood cell (WBC) count differential (absolute values)
- Hematocrit
- Hemoglobin
- Red blood cell (RBC) distribution width
- Mean corpuscular hemoglobin concentration
- Mean corpuscular hemoglobin
- Mean corpuscular volume
- Platelet count
- Prothrombin time with INR
- RBC count

11.1.6.2. Blood Chemistry

Samples will be collected before study drug dosing and after at least an 8-hour fast; however, in case of an early termination or recheck, subject fasting is not required prior to sample collection. The following tests will be performed:

- ALT
- Albumin
- ALP^a
- Amylase, total^a or pancreatic amylase
- Anion gap
- AST
- Bicarbonate
- Bilirubin (total, unconjugated, conjugated)
- Blood urea nitrogen
- Calcium
- Chloride
- Cholesterol (total, high-density lipoprotein [HDL], and low-density lipoprotein [LDL])
- Creatinine
- Creatine kinase^b
- eGFR, using CKD-EPI method
- Glucose
- HbA1c^c
- Lipase
- Phosphorus
- Potassium
- Sodium
- Triglycerides

^a Reflex fractionation, if greater than ULN

^b Reflex fractionation if greater than critical value

^c HbA1c will be collected at Screening, D28, EOS and ET

Subjects with normal ALT and bilirubin at baseline who have ALT >3 x ULN and bilirubin >2 x ULN OR subjects with elevated ALT at baseline who have ALT > 10 x baseline value and bilirubin >2 x ULN will also have serum gamma-glutamyltransferase (GGT) determined at the time these abnormalities are discovered. For these subjects, GGT may be repeated, as clinically indicated.

11.1.6.3. Urinalysis

Samples will be collected before study drug dosing and after at least an 8-hour fast; however, in case of an early termination or recheck, subject fasting is not required prior to sample collection. The following will be performed:

- Bilirubin
- Blood
- Color
- Glucose
- Ketones
- Leukocyte esterase
- Nitrites
- pH
- Protein
- Specific gravity
- Turbidity
- Urobilinogen
- Microscopic examination^a

^a Microscopic examination will be performed if dipstick test is positive for protein, blood, leukocyte esterase, or nitrites. (Microscopic examination includes bacteria, casts, crystals, epithelial cells, RBCs, and WBCs).

11.1.6.4. Drug Screen

A standard screen for drugs of abuse which includes testing for amphetamine, cannabinoids, opiates and cocaine will be performed for all subjects at the time points indicated in [Table 3](#), or as applicable.

11.1.6.5. Pregnancy Screen

Females of reproductive potential defined as women who have not been postmenopausal for at least 24 consecutive months (i.e., who have had menses within the preceding 24 months), or women who have not undergone surgical sterilization; specifically, hysterectomy, bilateral salpingectomy, bilateral oophorectomy, hysteroscopic sterilization, and/or tubal ligation, must have a negative pregnancy test at Screening, within the 24 hour period prior to Day 1 and at all other time points indicated in [Table 3](#), or as applicable. At Screening a serum beta human chorionic gonadotropin or urine dipstick pregnancy test will be performed. A urine dipstick pregnancy test will be performed at all other time points.

All post-menopausal females will have an FSH test at Screening.

11.2. Adverse and Serious Adverse Events

11.2.1. Adverse Events

An AE is defined as any untoward medical occurrence in a clinical study subject associated with the use of a drug (investigational or non-investigational) in humans, whether or not considered drug related. An AE can be any unfavorable and unintended sign (e.g., an abnormal laboratory

finding), symptom, or disease temporally associated with the use of a drug, without any judgement on causality. An AE can arise from any use of the drug (e.g., off-label use, use in combination with another drug) and from any route of administration, formulation, or dose, including overdose.

All AEs that occur after any subject has been consented, before treatment, during treatment, or up to and including the End of Study or Early Termination Visit, whether or not they are related to the study, must be recorded on forms provided by Hepion.

